5.2.5 Compliance

The Investigational Pharmacy site will complete required accountability and dosage preparation logs to be monitored by the MDACC IND Office. The existing clinical site's documentation system will capture all pertinent /required information on the preparation and administration of the dose.

5.3 Drug Storage and Drug Accountability

The study drugs will be shipped and stored at a temperature between 2° and 8 °C. The storage conditions stated in the investigator brochure may be superseded by the label storage.

The storage conditions and temperatures will be recorded on the Investigational Pharmacy temperature logs.

The Investigator or an approved representative (eg, pharmacist) will ensure that all investigational product is stored in a strictly controlled, secure area, at appropriate temperatures and in accordance with applicable regulatory requirements.

The Investigator or designated personnel must maintain adequate records documenting the receipt, use, loss or other disposition of the investigational product(s). Accountability Logs will be maintained by the Investigational Pharmacy. The forms must identify the investigational product, including batch or code numbers, and account for its disposition on a patient by patient basis, including specific dates and quantities.

Destruction of investigational product will be performed per the MDACC policy.

5.4 Concomitant Medications

Concomitant treatment considered necessary for the patient's well-being may be given at discretion of the treating physician.

All concomitant medications, blood products, as well as interventions (eg, paracentesis, etc.) received by patients from screening until the end of study visit will be recorded in the electronic medical record (EMR).

5.4.1 Other Anticancer or Experimental Drugs

No additional anticancer therapy will be permitted while patients are receiving one of the study drug combinations.

Additionally, the concurrent use of vitamins or herbal supplements should be considered with caution.

Palliative and supportive care for disease related symptoms may be administered at the Investigator's discretion.

5.4.2 Supportive Care

Palliative and supportive care for disease related symptoms may be administered at the Investigator's discretion and according to any available American Society of Clinical Oncology (ASCO) guidelines.

5.4.3 Hematopoietic Growth Factors

Primary prophylactic use of granulocyte-colony stimulating factors is not permitted during the first two cycles of treatment but they may be used to treat treatment emergent neutropenia as indicated by the current American Society of Clinical Oncology (ASCO) guidelines (J Clin Oncol, 2006. **24**(19): p. 3187-3205).

Erythropoietin may be used at the investigator's discretion for the supportive treatment of anemia.

5.4.4 Anti-inflammatory Therapy

Anti-inflammatory or narcotic analgesic may be offered as needed. Systemic anti-inflammatory therapies may be used to treat SAEs potentially related to the study drug(s). However, in such cases it is suggested that Investigators consult with a specialist based on the involved organ systems before instituting treatment.

5.4.5 Corticosteroids

Chronic, systemic corticosteroid (more than 10 mg/ day of prednisone equivalent) use for palliative or supportive purpose is not permitted. Use of corticosteroids as symptomatic treatment may be allowed on individual basis and upon discussion with the MDACC IND Office. Steroids for replacement therapy (physiologic replacement) are allowed. Acute emergency administration, topical applications, inhaled sprays, eye drops or local injections of corticosteroids are allowed.

5.4.6 Surgery

Caution is advised on theoretical grounds for any surgical procedures during the study. The appropriate interval of time between surgery and the study drug(s) required to minimize the risk of impaired wound healing and bleeding has not been determined. Stopping study drug(s) is recommended at least 14 days prior to surgery.

Postoperatively, the decision to reinitiate study drug(s) treatment should be based on a clinical assessment of satisfactory wound healing and recovery from surgery.

5.4.7 Radiation Therapy

Palliative radiotherapy to specific sites of disease is permitted if considered medically necessary by the treating physician. All attempts should be made to rule out disease progression in the event of increased localized pain. If palliative radiotherapy is needed to control bone pain, the sites of bone disease should be present at baseline, otherwise, bone pain requiring radiotherapy will be considered as a sign of disease progression.

The technique of radiation will be VMAT/IMRT for all arms. For Arm D, the treatment dose will be prescribed to the planning target volume (PTV) for all treatment groups. It is required that the prescribed isodose line should cover 100% of the internal gross tumor volume (IGTV) and more than 95% of the PTV. For central lung or liver lesion close to critical structures, compromised PTV coverage is allowed in order to meet normal tissue dose constraints, pending clinical judgments regarding optimal target coverage and normal tissues sparing by the treating physician.

There is no or little aperture margin recommended. The external border of the PTV will be covered by a lower isodose surface than usually used in conventional radiotherapy planning, which typically ranges from 70-95%. However, higher isodoses (hotspots) must be manipulated to occur within the target and not in adjacent normal tissue. Heterogeneity correction should be applied for planning.

5.4.7.1 Radiation Technique

Patients will be evaluated for regularity of breathing, responsiveness to feedback guidance, breath-hold capability. Based on this evaluation, a treatment delivery technique will be selected among the following:

1. Breath-hold (with or without feedback guidance).
2. Gated treatment.
3. Free-breathing (with or without feedback guidance).
4. Abdominal compression.
5. A combination of the above techniques.

A CT scan obtained using the same method of respiratory management as intended for treatment will be required for treatment planning purposes. This includes 4-dimensional CT (4DCT) for free-breathing, gated or abdominal compression techniques or repeated breath-hold CTs for breath hold techniques. Feedback guidance, including visual and/or audio techniques, will be used for all patients who would both benefit from and respond to training with such devices.

4DCT is a fast CT scan that capable of imaging tumor position during the entire breath cycle. A CT scan is obtained with the patient in each couch position for a whole breath cycle (usually lasting 5 to 6 seconds in each position) followed by repositioning to the next couch position. Following a scan, the computer resorts all images and reconstructs the tumor positions for an entire breath cycle, i.e., a movie file is created which captures organ movement throughout the breath cycle. Radiotherapy will be designed based on the path of organ motion captured by 4DCT.

5.4.7.2 Target Volumes

1. Gross Target Volume (GTV): Gross tumor as observed on a non-contrast CT should be delineated on lung (for lung tumors) or abdominal (for liver or adrenal tumors) windows from either 4DCT or repeated breath-hold CTs (see IGTV below).

2. Internal Gross Target Volume (IGTV): IGTV is the volume containing the GTV throughout its motion during respiration or positional variability during repeated breath holds. The motion during free breathing (with or without abdominal compression) will be determined from 4DCT, the variability of tumor location during breath hold will be determined by repeated breath hold CTs obtained on the same day. One method to combine the data from the multiple CT datasets is to create a maximal intensity projection (MIP) that is used as an aid to contour the IGTV. All CT datasets will be transferred to the treatment planning system for reference.

3. Clinical Target Volume (CTV) + Planning Target Volume (PTV): GTV plus 5-10 mm margin (based on physician discretion). Due to tight PTV margin, CTV margin is not recommended to be edited except when normal tissue toxicity is concerning based on treating physician's judgment. The prescribed dose of radiation (either 50 Gy or 60 Gy) will be dosed to the PTV, we recommend 95% coverage if possible.

5.4.7.3 Daily Treatment Setup

The appropriate immobilization will be chosen for each patient. Most patients will be immobilized with arms up using a commercially available vacuum immobilization bag that extends from the patient's head to their pelvis combined with a wing board.

On-board imaging: Daily on-board imaging such as CT on-rails, cone beam CT, or 4-D cone beam CT will be conducted prior to each radiation fraction. Position adjustment and target coverage confirmation will be performed daily based on imaging study. The setup uncertainty will be kept to less than a 3 mm (2 s) variation. This value is based on the uncertainties of the couch readouts added in quadrature with $\frac{1}{2}$ the voxel size of the CT. Adjustment of patient position is needed if target coverage is judged by the treating physician to be inadequate and/or critical normal tissues toxicity is concerning.

Repeated on-board CT after position adjustment is recommended if more than 5 mm shift is conducted.

5.4.7.4 Dose Volume Constraints

60 Gy in 10 fractions dose constraints (54-58):

- Spinal Cord: 40 Gy \leq 1 cc
- Lung: V20 \leq 20%, V10 $<$ 30%, V5 $<$ 50%
- Esophagus: 60 Gy \leq 1 cc, 40 Gy \leq 10 cc
- Trachea: 70 Gy \leq 1 cc, 60 Gy \leq 10 cc
- Main bronchus: 70 Gy \leq 1 cc, 60 Gy \leq 10 cc
- Heart: 70 Gy \leq 5 cc, 50 Gy \leq 10 cc
- Brachial plexus: 50 Gy \leq 1 cc, 40 Gy \leq 10 cc
- Major vessels: 70 Gy \leq 5 cc, 60 Gy \leq 10 cc
- Skin (defined as outer 0.5 cm of body surface): 60 Gy \leq 1 cc, 50 Gy \leq 10 cc
- Kidney: V50 \leq 33%

Please note that patients on Arm D will have radiation as part of the study treatment regimen combination.

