15. For Arm D, radiation will be given to 1-3 metastatic lesions. Radiation as described in Section 3.2 will be given during the Radiation Lead-in (Days -5 to -1) or 3 consecutive business days (+/-3 days). Cycle 1 Day 1 treatment should be within 3 days of last dose of radiation.
16. For Arm D, avelumab will be administered IV every 2 weeks starting on Cycle 1 Day 15 (and then Days 1 and 15 of Cycle 2 and beyond).
17. For Arm D, utomilumab (4-1BB) will be administered IV every 4 weeks starting on Cycle 1 Day 1 (Day 1 of every cycle).
18. CT, MRI, or PET-CT Scans will be performed at screening, then every 2 cycles or 8 weeks +/- 7 days for the first year of treatment. Thereafter tumor assessments will be performed every 3 cycles or 12 weeks +/- 7 days during treatment, independent of cycle delays.

19. Tumor markers (if applicable) will be collected at screening, then every 2 cycles or 8 weeks +/- 7 days for the first year of treatment. Thereafter tumor assessments will be performed every 3 cycles or 12 weeks +/- 7 days during treatment, independent of cycle delays.
20. For De-Escalation and MTD Expansion Cohort in Arm D, tumor tissue will be obtained pre- treatment (baseline), prior to Cycle 3 Day 1 dosing, and at progression (if achieved stable disease \geq 6 months, partial response, or complete remission) provided there is technically biopsiable tumor, and it is safe for patient to undergo biopsy.
21. For De-Escalation and MTD Expansion Cohort in Arm D, blood samples will be collected at baseline (prior to radiation), prior to Cycle 1 Day 1 dosing, prior to Cycle 1 Day 15 dosing, prior to Cycle 2 Day 1 dosing, prior to Cycle 3 Day 1 dosing, and at the time of progression (if patient had an initial response of stable disease \geq 6 months, partial response, or complete remission). Cell free DNA from patient's blood samples will also be analyzed.
22. Archival tissue may not be utilized for the baseline sample time point.

GLOSSARY OF ABBREVIATIONS

β-HCG	Beta human chorionic gonadotropin
1L	First Line Treatment
2L	Second Line Treatment
3L	Third Line Treatment
ADR	Adverse Drug Reaction
AE	Adverse event
ALC	Absolute lymphocyte count
ALT (SGPT)	Alanine aminotransferase
ANC	Absolute neutrophil count
aPTT	Activated partial thromboplastin time
AST (SGOT)	Aspartate aminotransferase
AUC	Area under the curve
BP	Blood pressure
BSA	Body surface area
BUN	Blood urea nitrogen
CA	Competent Authority
CDDP	Cisplatin
CHF	Congestive heart failure
CI	Confidence interval

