3.2.4 Arm D: Avelumab + Utomilumab (4-1BB) + Radiation

In the dose escalation phase, the dose of radiation will be de-escalated in combination with fixed doses of utomilumab (4-1BB) and avelumab to evaluate the safety, tolerability, and MTD in patients with advanced solid tumors.

Once the MTD or RP2D is determined, the Arm D MTD expansion will enroll up to 14 patients at the previously established safe dose for additional safety and correlative studies to establish the RP2D for this combination.

Radiation will be administered to 1-3 metastatic sites. This will be de-escalated from a total of 24 Gy to 21 Gy. The technique will be stereotactic radiation via intensity-modulated radiation therapy (IMRT) or Volumetric modulated arc therapy (VMAT). The radiation lead-in will occur within Days -5 to -1 with a +/- 3 day window. There will be 3 fractions or days of radiation. In all cases, the radiation must initiate and end within the radiation lead-time. Cycle 1 Day 1 study drug treatment should begin within 3 days of last dose of radiation.

Utomilumab (4-1BB) will be administered at the fixed flat dose of 100 mg IV on Day 1 of each 28-day cycle or every 4 weeks. Avelumab will be administered at the fixed dose of 10 mg/kg IV on Day 15 of Cycle 1 and Days 1 and 15 of each subsequent 28-day cycle or every 2 weeks. Premedications will be administered per institutional standard.

On days when both avelumab and utomilumab are administered, avelumab will be administered first.

Patients will be restaged at the end of every two cycles and tumor response evaluation will be based on RECIST 1.1 and irRECIST. Patients may be allowed to continue treatment after two cycles of avelumab combinations if there is continued clinical response or disease stabilization and patients do not have significant toxicities. Following radiation, a patient may continue treatment on this combination therapy until the patient experiences confirmed disease progression, unacceptable adverse event(s), intercurrent illness that prevents further administration of treatment, and/or treatment is discontinued following investigator's decision to withdraw the patient, pregnancy, patient withdraws consent, noncompliance with trial treatment or procedure requirements, or administrative reasons.

Table 6: Dosing for Arm D: Avelumab + Utomilumab (4-1BB) + Radiation

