Dose Level	Radiation Days -5 to -1	Utomilumab (4-1BB) IV Every 4 Weeks Starting Cycle 1 Day 1	Avelumab IV Every 2 Weeks Starting Cycle 1 Day 15
1 (Start)	24 Gy in 8 Gy / fraction for 3 fractions	100 mg	10 mg/kg
-1	21 Gy in 7 Gy/ fraction for 3 fractions	100 mg	10 mg/kg

As of Amendment Version 09, the avelumab and radiation dosing for Arm D was revised; therefore, the dose de-escalation was re-started.

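### The Arm D radiation planning rules carry a 50/60 Gy dose and 10-fraction organ limits that do not fit 24 or 21 Gy in 3 fractions

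*Combined protocol and SAP*

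**What the plan says.** **Dose levels.** Section 3.2.4 states the plan for total dose: "This will be de-escalated from a total of 24 Gy to 21 Gy". Table 6 gives the starting level as "24 Gy in 8 Gy / fraction for 3 fractions" and level -1 as 21 Gy in three 7 Gy fractions. One to three metastatic sites are treated in a lead-in on Days -5 to -1. Footnote 15 of the Arm D schedule points back to the same place: "Radiation as described in Section 3.2 will be given during the Radiation Lead-in".

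**Planning rules.** Section 5.4.7 opens with palliative radiotherapy and then turns to the study regimen: "For Arm D, the treatment dose will be prescribed to the planning target volume (PTV) for all treatment groups". The note under the organ limits in Section 5.4.7.4 also names Arm D. Within these rules:

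- Section 5.4.7.2: "The prescribed dose of radiation (either 50 Gy or 60 Gy) will be dosed to the PTV".
- Section 5.4.7.4 lists its organ limits under one schedule only: "60 Gy in 10 fractions dose constraints".
- Section 5.4.7, for central lung or liver lesions near critical structures: "compromised PTV coverage is allowed in order to meet normal tissue dose constraints", subject to the treating physician's judgment.
- Section 5.4.7 says the PTV border is covered by an isodose "which typically ranges from 70-95" percent, and that hotspots must lie inside the target.

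No 3-fraction limit and no rule for converting the 10-fraction limits appears anywhere.

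**The concern.** Two rules in a section that applies to Arm D do not fit the Arm D regimen. The 50 or 60 Gy sentence cannot be followed together with Table 6. The organ limits were written for a course with more than twice the total dose and more than three times as many fractions. A limit that the planned dose cannot reach constrains nothing, so the allowance to give up PTV coverage to protect normal tissue has almost no numeric trigger outside lung.

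The list also has no bowel or liver limit. Yet Section 5.4.7.2 foresees liver and adrenal targets, and Section 1.4 warns that irradiating bowel could worsen colitis.

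This touches a primary objective. Radiation is the only component de-escalated in Arm D, and the aim is to find the safety, DLTs and MTD of that level given with utomilumab and avelumab. If normal-tissue exposure at a nominal dose level is left to individual judgment, DLTs counted at that level are harder to interpret.

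A minor leftover points the same way. The first Arm D diarrhea bullet in Sections 5.2.4.2 and 5.4.7.5 describes weeks 3 to 5 of radiation with chemotherapy, which Arm D does not give. The other three bullets fit.

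**Working it through.** **1. The plan's own totals.** 8 Gy x 3 = 24 Gy and 7 Gy x 3 = 21 Gy, as in Table 6. The doses in Section 5.4.7.2 are 50/24 = 2.1 to 60/21 = 2.9 times these.

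**2. Count of limits in Section 5.4.7.4.**

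| Organ | Dose thresholds (Gy) |
|---|---|
| Spinal cord | 40 |
| Esophagus | 60, 40 |
| Trachea | 70, 60 |
| Main bronchus | 70, 60 |
| Heart | 70, 50 |
| Brachial plexus | 50, 40 |
| Major vessels | 70, 60 |
| Skin | 60, 50 |
| Kidney | 50 |
| Lung | 20, 10, 5 |

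That is 16 non-lung limits (three at 40 Gy, four at 50, five at 60, four at 70) plus 3 for lung, 19 in all. The lowest non-lung threshold is 40 Gy.

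**3. Highest dose from one site, no summed dose.**

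- *Normal tissue next to the target.* If the hotspot rule is met, this tissue gets at most about the prescribed dose. The gap to the lowest non-lung limit is 40 - 24 = 16 Gy at level 1 and 40 - 21 = 19 Gy at level -1. The rule is a planning instruction, not a guaranteed cap.
- *Tissue inside the PTV.* Assume 100% is the plan maximum, so maximum dose = prescribed dose / prescription isodose.

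| Level | 95% isodose | 70% isodose | Non-lung limits that can be exceeded | Isodose at which the maximum equals 40 Gy |
|---|---|---|---|---|
| 24 Gy | 24/0.95 = 25.3 Gy | 24/0.70 = 34.3 Gy | 0 of 16 | 24/40 = 60% |
| 21 Gy | 21/0.95 = 22.1 Gy | 21/0.70 = 30.0 Gy | 0 of 16 | 21/40 = 52.5% |

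Both break-even isodoses lie below the stated range.

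**4. If dose is summed.** Counting prescription dose only and assuming complete overlap:

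- Two sites give 48 or 42 Gy, which reaches 3 of 16 limits at either level.
- Three sites give 72 Gy (16 of 16) or 63 Gy (3 + 4 + 5 = 12 of 16). This is a theoretical case.
- An earlier course of 16 Gy (level 1) or 19 Gy (level -1) to the same tissue would also reach the 40 Gy limits. Exclusion criterion 22 bars high-dose overlap only within 3 months.

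The protocol has no rule for summing dose over sites or courses.

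**5. Lung.** The lung limits can bind but mean something different at the lower dose. In physical dose only, each cut-off as a share of the prescription is:

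| Limit | 60 Gy | 24 Gy | 21 Gy |
|---|---|---|---|
| V20 | 33% | 83% | 95% |
| V10 | 17% | 42% | 48% |
| V5 | 8% | 21% | 24% |

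**6. Patients affected.** Table 12 gives 33 for Arm D, of whom 4 and 3 were enrolled under earlier schedules: 33 - 4 - 3 = 26, which matches 12 (de-escalation, Section 9.3) + 14 (expansion, Section 3.2.4). Table 1 prints a maximum of 32. How many would be treated near a listed organ is unknown.

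**The case against.** The strongest reply is that this is leftover planning text with little practical effect. Table 6 gives total dose, fraction size and number of fractions. The schedule footnote sends users to Section 3.2, and a 10-fraction course does not fit a five-day lead-in. Nobody is likely to deliver 50 or 60 Gy. The limits go unreached because the dose is low, which is not in itself a hazard, and the list states its own schedule. Coverage and margins also rest on physician judgment. Daily imaging with a 3 mm setup limit, radiation-related DLTs, the 3+3 rules and the expansion stop above 33% all remain.

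Most of this is true. The intended dose is not in doubt, excess toxicity is not shown, and lung limits could apply to a liver target close to lung. But none of these safeguards is an organ dose limit, and none reconciles the 50/60 Gy sentence with Table 6.

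Nor does a lower total dose settle the matter, because Arm D gives 7 or 8 Gy per fraction against 6 Gy in the listed schedule. As an illustration only, take biologically effective dose = D(1 + d/(alpha/beta)), with D the total dose and d the dose per fraction; the documents give no alpha/beta. For 24 Gy in 3 fractions against 40 Gy in 10:

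- alpha/beta 2: 24(1 + 8/2) = 120 against 40(1 + 4/2) = 120.
- alpha/beta 3: 24(1 + 8/3) = 88 against 40(1 + 4/3) = 93.
- alpha/beta 10: 24(1 + 8/10) = 43 against 40(1 + 4/10) = 56.

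Level 1 at prescription dose would thus be at or below a converted 40 Gy limit. Level -1 is lower (94.5, 70 and 36). The margin depends on a conversion the protocol never states, and the conclusion here does not rest on it.

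**Conclusion.** The concern holds. Section 5.4.7.2 contradicts Table 6 on the prescribed dose, by a factor of 2.1 to 2.9. Section 5.4.7.4 gives only 10-fraction limits, and for a single site with no summed dose 0 of its 16 non-lung limits can be exceeded at either level. That result refers to physical dose as written. Inside the PTV it also assumes the 70-95% isodose range with 100% as the plan maximum. It no longer holds if sites overlap fully or enough earlier dose is added.

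The point must be fixed because a stated dose rule is wrong for the one component being de-escalated under a primary safety objective, in up to 26 patients. Whether any organ would be unsafe at 24 or 21 Gy cannot be derived from the documents and is not claimed.

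**What to change.** 1. In Section 5.4.7.2, replace the 50 or 60 Gy wording with a reference to the patient's dose level in Table 6.
2. In Section 5.4.7.4, replace the whole list, lung values included, with 3-fraction limits. Add bowel and liver if abdominal lesions may be treated. State how dose is summed over one to three sites and with earlier courses. The values are for the radiation oncologists to set.
3. Editorial: in the first diarrhea bullet of Sections 5.2.4.2 and 5.4.7.5, delete the week 3 to 5 wording. Keep the instruction to rule out other causes and the other three bullets.

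Cost: amendment wording and radiation oncology sign-off. No extra patients, visits or procedures.

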5.4.7.5 Radiation Breaks and Discontinuation

Radiation breaks will occur for radiation-related Grade \geq 3 toxicities uncontrolled by symptom management and medications pending judgment of the treating radiation oncologist. Continual re-evaluation will occur daily while a patient is on a radiation break until which time the treating radiation oncologist re-initiates the patient on radiation or discontinues treatment. Patients will be considered evaluable on the study if the planned radiation fractions were administered with $<$ 5 days of unplanned treatment breaks. Patients will be considered evaluable on the study if patients received 75% of radiation dose.

For Arm D, patients who experience:

- Grade 1 and 2 diarrhea related to radiation therapy and chemotherapy occurs in majority of patients starting around the end of the 3rd week of radiation therapy. Diarrhea prior to the 3rd week of radiation therapy is not usually associated with chemotherapy and radiation therapy and other causes need to be ruled out including C. Diff. This diarrhea lasts through the 5th week of radiation therapy and up to a week after the external beam radiation therapy is completed. This diarrhea is usually controlled with Imodium AD but sometimes Lomotil is used to control it. Grade 3 or higher diarrhea – not controlled with Imodium or Lomotil is rare – usually less than 2-3% in patients in patients receiving chemotherapy and radiation therapy.
- Grade 1 and 2 diarrhea related to radiation may continue avelumab or utomilumab (4-1BB) at the discretion of the physician,
- Grade 3 and 4 diarrhea related to radiation will hold avelumab or utomilumab (4-1BB). At the physician's discretion, avelumab or utomilumab (4-1BB) may continue at same dose if diarrhea improves to </= Grade 1.
- In case the event of diarrhea is suspected to be immune-related and/or in the case the event of diarrhea does not respond to the measures applied for radiotherapy-induced diarrhea and has an increase in severity, follow the toxicity management described for diarrhea/colitis in the immune-related adverse event toxicity management (Table 10).

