3.3 Dose-Limiting Toxicity (DLT) Definition

Severity of adverse events will be graded according to CTCAE version 4.03. For the purpose of dose de-escalation, a DLT is defined as any of the following adverse events occurring in the first 56 days following Cycle 1 Day 1 (dosing of PF-04518600 (OX40) and/ or Utomilumab (4-1BB)) of study participation during the dose de-escalation, unless there is a clear alternative explanation (eg, related to underlying disease/ progression):

- Discontinuation of a patient due a toxicity that is at least possibly study drug(s) and/or radiation related before completing DLT period.
- Delay by more than 4 weeks (28 days) in receiving the next scheduled cycle due to persisting toxicities attributable to the study drug(s) and/or radiation.
- Non Hematologic (all will be graded according to CTCAEv4.03 criteria):
 - Grade \geq 3 nausea/vomiting or diarrhea lasting \geq 72 hours while taking optimal supportive medications;
 - Grade \geq 3 fatigue lasting \geq 7 days;
 - Grade \geq 2 pneumonitis lasting \geq 7 days despite treatment with corticosteroids;
 - Grade \geq 3 rash lasting \geq 7 days despite treatment;
 - Grade \geq 3 immune related toxicities lasting \geq 7 days despite treatment with corticosteroids;

- Any other Grade ≥ 3 non-hematological toxicity (except for electrolytes abnormalities that are reversible and asymptomatic or hair loss which is not dose-limiting);
- Grade ≥ 3 AST, ALT, or total bilirubin elevation lasting ≥ 7 days.
- Hematologic:
 - Grade 4 neutropenia [absolute neutrophil count (ANC) $< 500/\text{mm}^3$] lasting ≥ 7 days;
 - Febrile neutropenia (ANC $< 1000/\text{mm}^3$ with a single temperature $\geq 38.3^\circ\text{C}$ or sustained temperature of $> 38^\circ\text{C}$ for over 1 hour);
 - Grade ≥ 3 thrombocytopenia associated with bleeding, or grade 4 thrombocytopenia;
 - Grade 4 anemia.

Elevation of amylase and/or lipase without clinical and/or radiographic evidence of pancreatitis are not considered DLT, and the patient can resume treatment at any grade at the discretion of the treating physician in consultation with the PI.

During the dose de-escalation portion (Arm D) of the study, patients who missed any doses during the DLT period for reasons unrelated to study drug are not evaluable for DLT and will be replaced.

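### The protocol contradicts itself on whether an Arm D patient whose radiation is stopped for toxicity counts in the 3+3 that sets the radiation dose

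*Combined protocol and SAP*

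**What the plan says.** Section 3.2.4 gives the Arm D radiation before Cycle 1 Day 1, in a lead-in on Days -5 to -1 (with a window of 3 days either way): "There will be 3 fractions or days of radiation". Table 6 has two levels, "24 Gy in 8 Gy / fraction for 3 fractions" and "21 Gy in 7 Gy/ fraction for 3 fractions", with both drugs fixed. Estimating the MTD for this arm is a primary objective (Section 2.1.1).

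Some passages can take a patient stopped for radiation toxicity out of the count:

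- Section 5.4.7.5 interrupts radiation for uncontrolled radiation-related toxicity of Grade 3 or higher, until "the treating radiation oncologist re-initiates the patient on radiation or discontinues treatment". It then gives two evaluability sentences. One begins "Patients will be considered evaluable on the study if the planned radiation fractions were administered with" and requires fewer than 5 days of unplanned breaks. The other is "Patients will be considered evaluable on the study if patients received 75% of radiation dose". Neither has a toxicity exception.
- Sections 3.3 and 3.4 run the DLT window for 56 days from Cycle 1 Day 1.
- Section 3.3 says that patients who miss doses in the DLT period "for reasons unrelated to study drug are not evaluable for DLT and will be replaced". Radiation is not named.
- Section 9.1 (Safety Analysis Set) replaces anyone not dosed at least once with each study medication. Avelumab starts only on Cycle 1 Day 15.
- The synopsis (Safety Assessments) asks for attribution of a DLT to the study drugs and omits radiation.
- Table 7 judges the MTD on 6 evaluable patients, and Section 9.3 foresees replacing inevaluable ones.

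Other passages keep the patient in:

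- The first two DLT bullets in Section 3.3 count discontinuation, or a delay of more than 4 weeks, from toxicity related to study drug or radiation.
- Section 3.3 also limits off-study replacement to reasons other than toxicity or progression.
- Section 3.5 considers all enrolled participants in the DLT analysis.

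**The concern.** A patient who cannot complete radiation because of its toxicity is the event that a radiation de-escalation exists to detect. If that patient is treated as inevaluable and replaced, exclusion depends on the outcome. The six patients left are those who tolerated all three fractions, and the cohort looks safer than the dose is.

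The cohort is small and the limit is one DLT in six, so the scoring of one patient can change the decision. Two teams applying different sections could score the same patient as a DLT or as a replacement, and reach different radiation MTDs.

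**Working it through.** **The plan's own figures.** Two levels of up to 6 patients give 2 × 6 = 12, as Section 9.3 states. The radiation totals agree: 3 × 8 = 24 Gy and 3 × 7 = 21 Gy. The documents state no operating characteristics for the 3+3.

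**What the 75% rule means with three fractions.**

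| Fractions given | Share of dose | Level 1 | Level -1 |
|---|---|---|---|
| 1 | 33.3% | 8 Gy | 7 Gy |
| 2 | 66.7% | 16 Gy | 14 Gy |
| 3 | 100% | 24 Gy | 21 Gy |
| 75% threshold | 75% | 18 Gy | 15.75 Gy |

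Only three of three passes.

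**Timing.** Section 3.2.4 requires radiation to start and end within the lead-in, and Cycle 1 Day 1 follows the last fraction. A stop during the radiation course therefore falls before the DLT window opens. The discontinuation bullet in Section 3.3 sits under that same window, so whether it reaches a lead-in stop is unclear. The Per Protocol set in Section 9.1 has no radiation-dose condition, but it uses the same 56 days and does not settle the point.

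**Effect on the MTD decision.** Under Table 7, level 1 is accepted with at most 1 DLT in 6:

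P(accept) = (1 − p)^6 + 6p(1 − p)^5.

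The two-stage sum P(0/3)·[P(0/3) + P(1/3)] + P(1/3)·P(0/3) gives the same value.

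Let s be the rate of radiation-stopping toxicity and d the rate of other DLTs. Both are assumptions, taken as independent. If all events count, p = 1 − (1 − s)(1 − d). If every stopper is dropped and replaced, p = d. With d = 10%, the second case gives 0.9^6 + 6 × 0.1 × 0.9^5 = 0.531 + 0.354 = 0.886.

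| s | p, all counted | P(accept), all counted | P(accept), stoppers dropped |
|---|---|---|---|
| 2% | 0.118 | 0.849 | 0.886 |
| 3% | 0.127 | 0.829 | 0.886 |
| 5% | 0.145 | 0.788 | 0.886 |
| 10% | 0.190 | 0.680 | 0.886 |
| 20% | 0.280 | 0.464 | 0.886 |

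With s = d = 20%, p is 0.36 and the pair is 0.301 against 0.655.

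**If only some are dropped.** When a share f of DLT patients is removed and replaced, the apparent rate is p(1 − f)/(1 − pf). At a true rate of 0.33, P(accept) is 0.358 when all count. It is 0.405 at f = 0.10, 0.488 at f = 0.25 and 0.661 at f = 0.50 (apparent rate 0.165/0.835 = 0.198).

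**The case against.** A reader might infer that the plan has a settled rule dropping and replacing patients whose radiation is stopped for toxicity. The documents do not support that. Section 5.4.7.5 mentions neither DLT evaluability nor replacement. It does not say what its patients are evaluable for, and it says if rather than only if. The passages in Sections 3.3 and 3.5 that keep such patients in are explicit. Within the window, most other Grade 3 or higher non-hematological toxicity is a DLT anyway, the principal investigator may class other worrying events as DLTs, and the IND Medical Monitor reviews each cohort summary. All of this stands, and it makes the defect a contradiction rather than a fixed exclusion.

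The clause on missed doses is also narrower than it looks. It covers the DLT period, so it does not ordinarily reach a missed lead-in fraction. It can reach drug doses withheld because of radiation toxicity.

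The size is open too. To fail the 75% rule, a toxicity must stop radiation before the third fraction, within days. The protocol's only related figure is under 2-3% for uncontrolled Grade 3 or higher diarrhea (Sections 5.2.4.2 and 5.4.7.5). It describes chemoradiation over several weeks, so it is only indicative, but rates of 10-20% should not be taken as expected.

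These points do not close the gap before Cycle 1 Day 1, and the replacement sentence in Section 9.1 has no toxicity exception.

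**Conclusion.** The concern holds as an unresolved contradiction. Where the evaluability, window and replacement rules are applied as written, radiation-limiting events can leave the evaluable six, and the decision is biased towards accepting the higher radiation level. Where the DLT bullets and the all-enrolled sentence are applied, those events count.

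The direction is clear, but the size is not. With other DLTs at 10% and every stopper dropped, the chance of accepting level 1 is overstated by about 4 points at a 2% stopping rate, 10 points at 5%, 21 at 10% and 42 at 20%. These are upper limits for each assumed rate, because dropping every stopper is the extreme reading. Because the ambiguity sits in the denominator of a primary safety decision, it should be settled before Arm D cohorts are scored.

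**What to change.** Reconcile the synopsis and Sections 3.3, 3.4, 5.4.7.5 and 9.1 with the first DLT bullet and off-study replacement rule of Section 3.3 and the all-enrolled sentence of Section 3.5:

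- **Section 5.4.7.5:** say what evaluable refers to. State that the 75% and 5-day criteria do not remove from the DLT denominator a patient who stopped radiation or missed a dose because of toxicity at least possibly related to radiation or study drug.
- **Section 3.3, replacement sentence:** extend the reasons to those unrelated to study drug or radiation.
- **Sections 3.3 and 3.4:** state that for Arm D, DLT observation includes the radiation lead-in from the first fraction. Carry the same window into the Per Protocol set in Section 9.1.
- **Section 9.1, Safety Analysis Set:** exempt toxicity-related cases from the replacement sentence.
- **Synopsis:** align DLT attribution with Section 3.3, which names radiation.

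These changes settle who is counted. They leave the doses, the DLT toxicity grades and the criteria for interrupting radiation as they are. The cost is a few sentences, with no extra patients or data. The downside is a possibly earlier de-escalation.
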